2.1.2 Secondary Objectives

- To describe the safety of Prepopik in children aged 9 years to 16 years through the collection of adverse events (AEs), clinical laboratory tests, and physical examination
- To describe the completion of prep as directed to colon cleansing by Prepopik in preparation from colonoscopy in children aged 9 years to 16 years
- To describe the tolerability and satisfaction of colon cleansing by Prepopik in preparation for colonoscopy in children aged 9 years to 16 years as assessed by a standardized subject questionnaire administered at the study site before colonoscopy
- To evaluate pharmacokinetic (PK) characteristics of Prepopik in children aged 9 years to 16 years

2.2 Endpoints

2.2.1 Primary Endpoint

• Proportion of subjects classified as success defined by "excellent" or "good" in the Aronchick scale

2.2.2 Secondary Endpoints

- Incidence of adverse events and abnormal findings in clinical laboratory test and physical examination
- Proportion of subjects who took the assigned dose for the IMP [investigational medicinal product]
- Frequency of each category of the Tolerability and Satisfaction Questionnaire
- PK exposure will be assessed utilizing a sparse sampling of subjects (Sparse sampling means no need for special PK time)

75

30

3 **Trial Design**

This study is a randomized, assessor-blind, multicenter, dose-ranging study. Subjects undergoing an elective complete colonoscopy will randomly receive one of the following products:

- Prepopik: 2 divided doses given the night before (first dose) and approximately 5 hours prior (second dose) to procedure. A dose is defined for one subset of subjects aged 9 years to 12 years as 1/2 sachet, for another subset of subjects aged 9 years to 12 years per randomization as 1 sachet and for subjects aged 13 to 16 years as 1 sachet.
- Oral PEG based preparation/local standard of care per appropriate label and/or • institutional instructions.

See Section 3.1.1 of the protocol for the trial design diagram.

3.1 **General Design Considerations**

This is an age-stratified, parallel-group design with three treatment arms in the younger ages and two treatment arms in the older ages as shown in Table 1.

able 1 Overview of Study Treatment Groups by Age				
	Age (Age Group		
Treatment Group	9-12 years	13-16 years		
Prepopik: 1/2 sachet	15	0		
Prepopik: 1 sachet	15	15		
Standard of care	15	15		

3.1.1 **Dosage Selection**

Total subjects

Selection of doses for this study are based on current dosages in Canada and the European Union. In Canada, current pediatric dosage is $\frac{1}{2}$ sachet (x2) for ages 9-12 years and 1 sachet (x2) for ages 13-18 years. This dosage has been studied in a well-controlled trial from the Toronto Hospital for Sick Children. It aimed to compare bowel preparation for colonoscopy in children with PicoSalax or PEG with electrolyte solution. Thirty five of PicoSalax patients (81%) were satisfied or very satisfied with the clean out compared with 19 (48%) in the PEG group (p=.001).7 The current dosages used in pediatrics in the European Union for ages 9-18 years is 1 sachet (x2). Therefore, in our study, the younger group (ages 9-12 years) will compare adult dose (1 sachet x2 as in the European Union) and $\frac{1}{2}$ the adult dose (1/2 sachet x2, Canadian dose) while the older group (ages 13-16 years) will use the adult dose.

45

3.1.2 Blinding

Blinding treatment to the endoscopist and his/her assistant(s) assessing the efficacy of the tested preparations removes possible bias. A placebo-controlled design would not be practical or ethical in this study as subjects would be required to have a second colonoscopy.

The integrity of blinding will be further preserved by requiring each subject or parent/guardian and the unblinded coordinator to sign a nondisclosure affidavit form instructing subjects/parents/guardians and the unblinded coordinator not to disclose the treatment groups.

3.2 Determination of Sample Size

Approximately 6-8 sites in the US are planned. A sufficient number of subjects will be screened to ensure up to approximately 75 (~15 subjects per treatment arm).

A total of at least 45 subjects will be exposed to Prepopik. In the two Phase 3 studies for adults, 83% and 84.2% of subjects were classified as success after bowel preparation with Prepopik. With 45 subjects, if 80% of subjects are classified as success in this study, the exact 95% confidence interval of the success rate will be calculated as 65% - 90%.

4 Subject Disposition

All subjects screened will be accounted for. The number of subjects screened but not randomized/allocated to treatment will be presented with the reason(s) for screen failure in a data listing.

The number and percentage of subjects randomized, beginning treatment, having a colonoscopy, completing, and withdrawing from the study will be tabulated for each treatment group, overall and by age group. The denominator for the percentages is the total number of subjects in the given treatment group, or the combined sample as appropriate. Reasons for early withdrawal will be tabulated by treatment group. Individual subject listings of study completion information will be produced, including the reason for early withdrawal.

The number of subjects included and excluded from safety and efficacy populations will be summarized for each treatment group. In addition, the reason(s) for exclusion from each population will be summarized. Individual subject listings of reasons for exclusion from the analysis populations will be produced. In addition, a separate subject listing of any eligibility violations will be produced.

The number and percentage of subjects randomized, treated, completing/withdrawing from the study and included/excluded from safety and efficacy populations will also be tabulated by study site.

5 **Protocol Deviations**

Major and minor protocol deviations will be defined and documented prior to database lock. Major protocol deviations which exclude the subject from the PP analysis set will include the following:

- Key violations of the protocol inclusion or exclusion criteria
- Significant violation of the dosing regimen as recorded on the eCRF including the amount of study preparation, and timing of receiving study medication
- Receiving study medication other than randomized assignment
- Taking exclusionary medications during the study and/or prior to the procedure, as described in the protocol. Exclusionary medications include:
 - o Lithium
 - Laxatives (suspended for 24 hours prior to procedure)
 - Constipating drugs (suspended for 2 days prior to procedure)
 - Antidiarrheals (suspended for 72 hours prior to procedure)
 - Oral iron preparations (suspended for 1 week prior to procedure)

6 Analysis Sets

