Subjects randomized to the "Split Dose" Prepopik group will begin treatment ( $1^{st}$  dose) 1 day before colonoscopy between 5:00 and 9:00 PM, and will complete the treatment ( $2^{nd}$  dose)  $\geq 6$  hours after on the next day, and at least 5 hours prior but no later than 9 hours prior to colonoscopy. Additionally, if the subject is in the hospital, instructions will be written to follow as close as possible the aforementioned dosage schedule. Prepopik is reconstituted by mixing the powdered contents of the sachet in a cup with approximately 5 ounces of cold water. Following each administration of Prepopik, subjects will consume approximately five 8 ounce glasses of clear fluids after the first administration and at least three 8 ounce glasses of clear fluids after the second administration. For "Day Before" Prepopik and fluids see section 5.

Subjects randomized to the oral PEG based preparation/local standard of care will follow appropriate label and/or institutional instructions.

[figure not shown]
On the day before the procedure (24 hours prior), all subjects will be limited to a liquid diet only. Special meal instructions for diabetic subjects are provided in APPENDIX 2. The coordinator who dispenses the drug will instruct the subject and his/her parent/guardian about the exact requirements during the Randomization Visit (Visit 2).

Subjects will return to the site  $5 \pm 2$  days following their colonoscopy for a laboratory sample (chemistry, hematology and coagulation). Subjects/parents or guardians will have a telephone assessment on Day 28 after the colonoscopy procedure.

Efficacy of the tested preparations will be evaluated by an assessor-blinded endoscopist using the Aronchick scale for overall colon cleansing. A standardized subject questionnaire administered on the day of colonoscopy and prior to sedation and the procedure will assess tolerability and satisfaction of the product (to be filled out by the subject and/or guardian).

Supersedes: 4 Page 21 of 65

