### 3.5.2 Selection of Endpoints

The primary endpoint, overall colon cleansing prior to colonoscopy, will be assessed by a blinded assessor endoscopist using the Aronchick scale. The Aronchick scale is a validated instrument that has been widely used and universally accepted, and has been previously used in pivotal trials that led to new drug application (NDA) approval, including the approval of HalfLytely. However, this study will compare Prepopik to oral PEG local standard of care preparations. Essentially, each endoscopic center has its own preparation concoction based on some combination of diet PEG 3350 sports drinks, enemas and stimulant laxatives.

Each investigational site will be trained on the use of the Aronchick Scale both at the investigator meeting and at initial site visit; subjects will not be initiated until all assessing gastroenterologists involved in the study at the investigational site are confident in using this tool.

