# 4.3.2 Prohibited Therapy

The following medications exclude subjects' participation in the study and/or must be suspended prior to the procedure:

- 1. Lithium
- 2. Laxatives (suspend for 24 hours prior to procedure. Laxatives as part of the SOC colonoscopy prep are not prohibited.)
- 3. Constipating drugs (suspend for 2 days prior to procedure)
- 4. Antidiarrheals (suspend for 72 hours prior to procedure)
- 5. Oral iron preparations (suspend for 1 week prior to procedure)

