### 5.5.2 Assessment of Compliance

Subjects will be considered compliant if dosing occurs within ±30 minutes of specified timings. The time of administration will be provided to the subject/parent/guardian by the coordinator who dispenses the drug and will be verbally confirmed with the coordinator. Subject's response to "Have you taken the medication within specified time periods?" will be documented in the CRF by the coordinator during the procedure visit (Visit 3).

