6.2 Per Protocol Analysis Set

Subjects with major protocol deviations that potentially impact efficacy will be excluded from the PP (per-protocol) analysis set. Subjects not taking the study medication in the prescribed time intervals will be excluded from the PP analysis set. These subjects will be identified prior to breaking the study blind. Analyses for the PP will be conducted according to the randomized treatment.

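### Do the laxative and dose-timing rules for the per-protocol set need rewriting before analysis?

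*SAP*

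**What the plan says.** **Laxatives.** SAP section 5 names the major deviations that remove a subject from the PP set. One is "Taking exclusionary medications during the study and/or prior to the procedure, as described in the protocol". The list under it includes "Laxatives (suspended for 24 hours prior to procedure" and stops there. Protocol 4.3.2 and the synopsis give the same 24-hour rule, then add "Laxatives as part of the SOC colonoscopy prep are not prohibited". Protocol 3.5.2 says each centre's SOC preparation is "some combination of diet PEG 3350 sports drinks, enemas and stimulant laxatives", so the exemption matters for the reference arm.

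**Timing.** SAP section 5 also excludes for "Significant violation of the dosing regimen as recorded on the eCRF including the amount of study preparation, and timing of receiving study medication". SAP section 6.2 has no such qualifier: "Subjects not taking the study medication in the prescribed time intervals will be excluded from the PP analysis set". Protocol 9.4.2 contains that same sentence. Protocol 5.5.2 adds a tolerance: "Subjects will be considered compliant if dosing occurs within ±30 minutes of specified timings". Neither PP definition mentions it. The second-dose timing varies between places; one form, in the synopsis and protocol 3.1, is "at least 5 hours prior but no later than 9 hours prior to colonoscopy".

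**Role of the PP set.** SAP 9.2 makes the ITT population primary and the PP population supportive. The primary objective is descriptive.

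**The concern.** A programmer who builds the PP flag from the SAP list alone would find no exemption. SOC subjects who followed their centre's instructions exactly could be excluded because that preparation contains a stimulant laxative. The losses would fall on one arm only and would cluster by site.

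The timing question is separate. If any dose outside the prescribed interval excludes, the word significant in SAP 5 does nothing for timing. If only a significant violation excludes, SAP 6.2 says too much. The prescribed interval is itself stated in more than one form. Take a second dose assigned for 5 h before colonoscopy and taken at 4 h 45 min. It is 15 minutes off its assigned time, so protocol 5.5.2 calls it compliant. It is 15 minutes inside the near limit quoted from protocol 3.1. SAP 6.2 would exclude it if no tolerance applies, and SAP 5 leaves it to judgment. At stake are the make-up and size of the PP set, and with them the only second analysis set planned for the primary endpoint.

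**Working it through.** **1. Laxatives: the two texts side by side**

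- The SAP bullet is not a free-standing rule. Its lead-in takes exclusionary medications as the protocol describes them, and the protocol describes them with the exemption in two places.
- SAP section 12 lists the changes from the protocol analyses: added 90% intervals, orthostatic summaries and PK summaries. Removal of the exemption is not among them.
- The bare reading defeats itself. Protocol 1.1 describes Prepopik as a stimulant cathartic plus an osmotic laxative, and the Split Dose regimen puts the second dose on the day of the procedure. Applied without reference to the protocol, the rule would exclude those Prepopik subjects too. No analyst would take that as the intended PP set.
- SAP 6.2 further limits exclusion to major deviations that could affect efficacy.

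**2. Timing: where the second dose is described** (hours before colonoscopy)

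| Place | Near limit | Far limit |
|---|---|---|
| Synopsis; protocol 3.1, later text | 5 h or more | 9 h, worded as quoted above |
| Protocol 3.1, opening bullet; SAP 3 | about 5 h | none given |
| Protocol 3.5.5 | 5 h or more | none given; refers to Section 5 |
| Protocol 5.1 | about 5 h | 9 h |
| Protocol Table 6-1, footnote f | 5 h or more | 9 h |

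The wording differs, and protocol 3.1 differs within itself. SAP 3 repeats the opening bullet of protocol 3.1, so it is not a new departure. Where 3.5.5 gives no far limit, it refers the reader to Section 5 for complete instructions. The quoted far limit, taken literally, would leave the near limit beside it with no function.

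**3. How SAP 5 and 6.2 combine**

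SAP 5 says what major deviations will include, and 6.2 adds a timing exclusion in its own sentence. Every significant timing violation is also a dose outside the interval, so applying both rules gives the 6.2 result. That is also the protocol 9.4.2 result.

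**4. What the analyst will have in hand**

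- Assigned administration times are given at Visit 2 (protocol 6.2). The 30 minutes in 5.5.2 attach to specified timings, not to the edges of a window.
- The CRF records whether medication was taken in the specified periods (protocol 5.5.2). Dose times and adherence to the time frame are listed (SAP 8) and summarized (SAP 8.1.2).
- The Day Before option has its own schedule in protocol 5.1. SOC subjects follow label or institutional instructions, and the solution, type and timing are documented (protocol 5.2.2).
- Deviations are defined before database lock (SAP 5), PP exclusions are identified before unblinding (SAP 6.2), and reasons for exclusion are summarized and listed (SAP 4).

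**5. Size**

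The plan's own figure comes first. For 36/45 = 80%, the exact (Clopper-Pearson) 95% interval is 65.4% to 90.4%, which matches the stated 65% - 90%.

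For all Prepopik against all SOC, assume 80% success in both groups. The half-width is 1.96 × √(0.16/n₁ + 0.16/n₂).

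- Planned numbers, 45 v 30: 1.96 × √(0.003556 + 0.005333) = 18.5 points.
- One site's SOC subjects lost, assuming equal enrolment over the planned 6 to 8 sites: 30/8 = 3.75 to 30/6 = 5 subjects. At 45 v 26 the half-width is 19.3 points, and at 45 v 25 it is 19.6.
- Nine Prepopik subjects lost on timing, 36 v 30: 19.4 points.

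The documents give no loss fraction, so these are illustrations. The SOC losses would arise only under the reading rejected in step 1.

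**The case for a change.** The best case for a change is that it costs one clause and one sentence, and that a cross-reference is weaker than a stated rule. PP is the only other analysis set for the primary endpoint, and the same undefined time frame feeds the compliance table in SAP 8.1.2. There is also a blinding point. Whether a laxative belonged to the SOC preparation depends on the arm, yet PP exclusions must be identified before the blind is broken, so case-by-case judgment is less safe than a written rule. Larger assumed losses would matter more: with a third of SOC subjects gone (45 v 20) the half-width is 21.1 points, and with two thirds gone (45 v 10) it is 27.4.

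Part of this stands. The word significant is undefined, neither PP definition says whether the 30 minutes apply, and the 4 h 45 min case has no single written answer. The differing second-dose passages are a real inconsistency and must be reconciled.

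The rest carries less weight. The larger losses need the laxative list to be applied against its own lead-in. The blinding point is met by fixing the definition before lock, as SAP 5 already requires, with the exemption taken from the protocol. The compliance table is descriptive, and the underlying dose times are listed, so readers can apply another tolerance.

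**Conclusion.** The concern does not hold as a reason to change the analysis plan. The laxative part is closed by the SAP's reference to the protocol; repeating the exemption would be optional tidying. The timing part is missing detail that the study team can settle when it defines deviations before lock, from assigned times, recorded dose times and one common sentence in SAP 6.2 and protocol 9.4.2. The second-dose passages must be reconciled as document upkeep, and no view is taken here on which is right.

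The effect on the primary ITT analysis is nil: membership depends on randomization alone, and no timing or medication rule enters it. For the supportive PP analysis, the illustrated cases of one site's SOC subjects or nine Prepopik subjects lost add about 0.8 to 1.1 points to an 18.5-point half-width (19.3 − 18.5 = 0.8; 19.6 − 18.5 = 1.1). This rests on 80% success in both groups, equal enrolment over sites, and loss counts that the documents do not give. It also assumes that the PP definition is fixed before unblinding, as the SAP states.

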6.1 Intention-To-Treat Analysis Set

The ITT analysis set will include all subjects who are randomized independent of whether or not the subject receives study treatment dose. Subjects who do not have an efficacy assessment for the data (Aronchick Scale) will be scored as a non-responder. Analyses for the ITT will be conducted according to the randomized treatment.

6.2 Per Protocol Analysis Set

Subjects with major protocol deviations that potentially impact efficacy will be excluded from the PP (per-protocol) analysis set. Subjects not taking the study medication in the prescribed time intervals will be excluded from the PP analysis set. These subjects will be identified prior to breaking the study blind. Analyses for the PP will be conducted according to the randomized treatment.

6.3 Safety Analysis Set

All subjects consuming at least one dose of study medication will be included in the Safety Analysis Set. Analyses for the Safety Dataset will be conducted according to the treatment actually received.

6.4 Pharmacokinetics Analysis Set

The pharmacokinetic (PK) analysis set will include all subjects from whom PK samples are obtained.

7 Trial Population

7.1 Demographics and Other Baseline Characteristics

Descriptive statistics of demographics, and other baseline characteristics will be presented for the ITT, PP and safety populations by treatment group, overall and by age group. For quantitative variables, all summaries will include the sample size, mean, median, standard deviation, minimum, and maximum. For the qualitative variables, the summaries will include the number and percentage of subjects for each outcome.

7.1.1 Demographics

The demographics variables to be summarized are: age in years, age group (9-12, 13-16), race, ethnicity, child-bearing potential, height and weight.

7.1.2 Vital Signs at Baseline

Baseline vital signs include systolic and diastolic blood pressure and pulse in the supine and standing positions. The change from supine to standing in systolic and diastolic blood pressures will also be presented as a measure of orthostatic change.

7.1.3 Laboratory Parameters at Baseline

The baseline laboratory parameter assessments include the blood chemistry, hematology, and coagulation test values.

7.2 Medical History

Medical history will be coded using MedDRA version 16.1 or later. Summaries will be presented by preferred term within System Organ Class for each treatment group, overall and by age group.

7.3 **Prior and Concomitant Medications and Other Safety Evaluations**

Prior and concomitant medications will be coded using the latest version of the World Health Organization (WHO) Drug Reference List. Summaries will be presented by preferred terms within Anatomic-Therapeutic-Chemical (ATC) class 1 and 2 for each treatment group, overall and by age group.

Separate summaries will be generated for prior medications and concomitant medications. Prior medications and concomitant medications are defined as follows:

- *Prior medications* are medications taken exclusively before receipt of study treatment. That is, the stop date of the medication is before the date of first study treatment administration.
- *Concomitant medications* are medications taken during the treatment period. That is, the medication was not stopped before the date of first study treatment administration AND was not started after the last visit date (i.e., visit 6).

If the timing of the dose of a medication cannot be established in relation to the start of study treatment administration, it will be considered as concomitant medication.

7.4 **Physical Examination**

Physical examination findings (normal, abnormal; clinically significant or not) will be summarized by treatment group, overall and by age group.

8 Exposure and Treatment Compliance

The date and time of each dose of study treatment, the number of glasses of liquid, the number of glasses of water and whether the doses were administered within the correct time frame will be listed.

8.1.1 Extent of Exposure

The number and percentage of subjects receiving each dose of study treatment will be summarized by treatment group, overall and by age group for the Safety analysis set.

8.1.2 Treatment Compliance

The number and percentage of subjects taking each dose within the specified time frame, as well as the required number of glasses of liquid will be summarized by treatment group, overall and by age group. The number of glasses of liquid and number of glasses of water will be summarized by the number of non-missing values, mean, median, minimum, maximum, and standard deviation by treatment group, overall and by age group.

9 Efficacy

